Description of Sleep Health Using the Internet (SHUTi) program for CBT-I. The SHUTi program is an automated, interactive, internet-based intervention based on well-established face-to-face CBT-I components including sleep restriction, stimulus control, sleep hygiene, cognitive restructuring, and relapse prevention. It consists of six core areas of focus that include interactive educational content and case studies about insomnia and its precipitating factors. These cores are designed to parallel traditional (in-person) CBT-I sessions and are “metered;” that is, new cores are available seven days after completion of the previous core. The program includes a variety of interactive features, including goal-setting, feedback based on user-identified symptoms, animations, quizzes, vignettes, and video-based expert explanations. SHUTi was developed based on the Model for Internet Interventions (a-Ritterband, et al., 2009). SHUTi users must fill out at least five daily sleep diaries for each core in seven days in order to access subsequent cores. Sleep diary input is crucial in the customization of the program based on individual situations.

SHUTi is considered a NSR IDE device as it is **not** being used in the indications as set forth:

- as an implant and presents a potential for serious risk to the health, safety, or welfare of a subject;
- purported or represented to be for use supporting or sustaining human life and presents a potential for serious risk to the health, safety, or welfare of a subject;
- for a use of substantial importance in diagnosing, curing, mitigating, or treating disease, or otherwise preventing impairment of human health and presents a potential for serious risk to the health, safety, or welfare of a subject; or
- Otherwise presents a potential for serious risk to the health, safety, or welfare of a subject”.

Protocol Number: 18-CC-0079

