1.1 Theoretical framework

This study will examine sleep-related beliefs and behaviors in the context of the Social Cognitive Theory (SCT; Bandura, 1986). Self-efficacy is perhaps the most well-established construct in the SCT and was an important predictor of sleep quality in our pilot work (Brooks et al., *Under Review*). We anticipate that the SHUTi program will directly impact personal, environmental, and behavioral factors for participants, and the theory includes all three as potential predictors of outcomes (insomnia severity and ultimately relapse).

1.2 Study Objectives:

1. *Phase I:* Assess the feasibility and acceptability of Internet-based CBT-I among individuals with AUD in recovery
2. *Phase II:* Compare the efficacy of CBT-I versus an education-only control group with respect to primary and secondary outcome variables
 - a. Primary outcome variables include: changes in insomnia severity over time, changes in actigraphy-recorded sleep efficiency over time
 - b. Secondary outcome variables include actigraphy-related (objective) variables, alcohol consumed (post-discharge), alcohol craving (post-discharge), sleep disturbance, daytime sleepiness, anxiety/depression, fatigue, self-efficacy for sleep, dysfunctional beliefs about sleep, and functional outcomes
 - c. Explore specific domains associated with improved outcomes: e.g. demographic, psychiatric, and/or drinking-related factors

2 Study design and methods

This is a two-phase study. Phase I will be focused on assessing feasibility and effectiveness of program delivery and data collection (n=10). Phase II will be a pilot RCT powered to examine intervention

Protocol Number: 18-CC-0079

effectiveness in the target population (n=20 per group). All study participants will receive a handheld tablet to access the SHUTi or education-only program.

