Dysfunctional Beliefs and Attitudes about Sleep (brief version; DBAS-16). The DBAS-16 is a 16-item questionnaire that assesses sleep-related cognitions including faulty beliefs and appraisals, unrealistic expectations, and perceptual and attention bias. The DBAS-16 has adequate internal consistency (Cronbach's alpha = 0.77 for clinical and 0.79 for research samples) and temporal stability ($r = 0.83$). Factor structure is similar to the original 30-item version of the questionnaire and includes perceived consequences of insomnia, worry/helplessness about insomnia, sleep expectations, and medication. Domains include expectations about sleep requirements and issues with being worried or feeling helpless about insomnia (Morin, Vallieres, & Ivers, 2007). The scoring of the DBAS-16 is the average score of all items.

Inventory of Depressive Symptoms (IDS; 30-item self-rated version). The IDS is a 30 item measure that can be used to screen for depression or measures symptom severity using the nine symptom domains used to define a major depressive episode. The IDS has high internal consistency (Cronbach's alpha = 0.90; Trivedi et al., 2004). Administration of the IDS takes approximately 10-15 minutes and scores are calculated by summing responses the 28 of the items for a score ranging from 0 to 84. A higher score indicates higher severity of depressive symptoms, with 49-84 indicating very severe symptoms (Rush et al, 2003, Trivedi et al, 2004).

Trait Anxiety Inventory. The Trait Anxiety Inventory is a 20-item measure of anxiety (Spielberger et al., 1983). The Trait Anxiety Inventory differs from the State Anxiety Inventory by asking questions on how respondents "generally feel" (Trait Anxiety), while the State Anxiety questionnaire asks how respondents feel "at this moment." Responses to each statement is rated on a four point scale, ranging from "almost never" to "almost always". The Trait Anxiety Inventory demonstrates high internal

Protocol Number: 18-CC-0079

consistency (Cronbach's alpha > 0.86) (Barnes, Harp, & Jung, 2002). Higher scores on the STAI indicates higher levels of anxiety.

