2.5 Inclusion and Exclusion Criteria

2.5.1 Participants will be eligible for this study if they:

- Are 18 – 65 years old
- A score of 10 or higher on the Insomnia Severity Index*
- Are admitted as a treatment-seeking inpatient on 1SE under protocol 14-AA-0181 (signing both the clinical and research consent)
- Have been inpatient for at least 14 days prior to consent/screening
- Can speak, understand, and write in English
- Are able to comply with study requirements (including ability to access the Internet at least 2x per week)

2.5.2 Participants will be ineligible for this study if they:

- Are pregnant
- Are a prisoner
- Report a physician diagnosis of moderate to severe obstructive sleep apnea (OSA) OR test positive for moderate to severe OSA as documented with an Apnea Hypopnea Index of 15 events/hour based on WatchPAT testing results
- Have irregular sleep schedules that prevent the ability to follow treatment recommendations (i.e. usual bedtimes outside of 8:00 pm to 2:00 am or arising times outside of 4:00 am to 10:00 am)
- Meet SCID-5/DSM-5 criteria for opioid use disorder in the past year
- Meet SCID-5/DSM-5 criteria for severe cocaine use disorder and/or severe cannabis use disorder in the past year
- Meet diagnostic criteria for an unstable or serious psychiatric condition (schizophrenia, bipolar, major depressive disorder not currently in remission) - based on diagnosis from the SCID for DSM-5
- Are participating in any experimental pharmacological intervention study
- Presence of unstable or serious medical/neurologic illness at PI and MAI discretion

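### Depression is scored as the full IDS total, which by its stated basis includes sleep symptoms, so a between-arm difference cannot by itself be read as a mood benefit

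*Combined protocol and SAP*

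**What the plan says.** Section 1.2 (objective 2b) names the Phase II secondary outcomes, among them "sleep disturbance, daytime sleepiness, anxiety/depression, fatigue, self-efficacy for sleep". Depression thus stands beside sleep disturbance and fatigue as a separate outcome.

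Section 2.4 measures it with the self-rated IDS, which "measures symptom severity using the nine symptom domains used to define a major depressive episode"; "scores are calculated by summing responses the 28 of the items for a score ranging from 0 to 84". The Table of Measures schedules the IDS at pre-test and post-test. Section 3 tests secondary objectives with a mixed model for repeated measures and sets significance at p<0.05.

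Three other statements bear on the reading:

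- Section 2.5.1 requires "A score of 10 or higher on the Insomnia Severity Index".
- Section 2.5.2 excludes "major depressive disorder not currently in remission", judged by the SCID for DSM-5.
- Section 1 (Background) describes SHUTi as built from "sleep restriction, stimulus control, sleep hygiene, cognitive restructuring, and relapse prevention".

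No section provides an IDS score without sleep items, a mood subscale, or a sensitivity analysis for the overlap.

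**The concern.** The treatment acts on sleep, everyone enters with insomnia symptoms, and the depression scale is built on domains that include sleep disturbance. If SHUTi improves sleep and leaves mood alone, the IDS total can still fall more in the SHUTi arm. That fall would be the primary insomnia effect seen a second time.

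The risk lies in interpretation. Because section 1.2 lists depression as its own outcome, a reader will take an IDS difference as separate evidence. Section 1 also cites earlier work in which internet CBT-I, and SHUTi itself, improved depressive symptoms, so a mood interpretation would come easily. As planned, the analysis has no means of telling the two explanations apart.

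**Working it through.** **Inputs from the documents.** IDS: 28 scored items, range 0 to 84 (section 2.4). Planning values: correlation 0.6, two-sided alpha 0.05, power 0.8, attrition 40%, 60 participants, detectable effect 0.84, equal allocation (section 3, written for the ISI).

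**Reproducing the plan's figures.**

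- IDS range: 84 / 28 = 3, so each item runs 0 to 3. The stated range is consistent.
- Completers: 60 × (1 − 0.4) = 36, or 18 per arm.
- SD of change, in units of the outcome SD: √(2 × (1 − 0.6)) = 0.894.
- Detectable effect: (1.960 + 0.842) × 0.894 × √(2/18) = 0.835, in agreement with the stated 0.84.

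Neither figure is in dispute. No power statement exists for the IDS, so the same planning values are borrowed for it below.

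**Assumptions, since the documents list no IDS items and give no IDS SD.** Sleep items: 1 to 4 of the 28. IDS SD: 5, 8 or 12. Between-arm difference arising on sleep items only: 1 to 4 points (4 points needs at least two sleep items).

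**Sleep items' share of the scale.** One item: 3/84 = 3.6%. Four items: 12/84 = 14.3%.

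**Their share of an observed score** depends on the non-sleep total, which is unknown. With 4 to 8 sleep points:

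- non-sleep total 10: 4/14 = 29% to 8/18 = 44%;
- non-sleep total 20: 4/24 = 17% to 8/28 = 29%.

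**Chance that a sleep-only difference reaches p<0.05.** Let D be the difference in points. The standardised shift is D/SD. Its standard error is 0.894 × √(2/18) = 0.298. The chance of significance in SHUTi's favour is Φ((D/SD)/0.298 − 1.960), a normal approximation. With no shift at all it is 2.5%.

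| D (points) | SD 5 | SD 8 | SD 12 |
|---|---|---|---|
| 1 | 0.20 SD, 10% | 0.12 SD, 6% | 0.08 SD, 5% |
| 2 | 0.40 SD, 27% | 0.25 SD, 13% | 0.17 SD, 8% |
| 3 | 0.60 SD, 52% | 0.38 SD, 24% | 0.25 SD, 13% |
| 4 | 0.80 SD, 77% | 0.50 SD, 39% | 0.33 SD, 20% |

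For D of 2 to 4 points, the shift runs from 0.17 to 0.80 SD and the chance from 8% to 77%. D is a difference between arms. If sleep items fall by 3 points on SHUTi and by 2 in controls, D is 1 and the top row applies.

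**The case against.** The case against has several parts, and most of them limit the point.

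- **The overlap is not spelled out.** Section 2.4 lists neither the nine domains nor the items. That sleep disturbance is among them follows from the definition of a major depressive episode that section 2.4 invokes, and the protocol diagnoses by DSM-5. The link is sound, but the number of sleep items has to be read off the form in use.
- **A reader might infer that sleep items dominate the score.** The documents do not show this. At most 14.3% of the range is theirs under the assumptions above. A larger share of the observed score needs low non-sleep scores, and the exclusion does not guarantee those: it removes only major depressive disorder not in remission. Remitted and subthreshold depression stay eligible, and section 1 calls depression a common comorbidity in alcohol use disorder.
- **Controls may improve too.** Section 1 reports pilot data in which sleep disturbance fell from 90% at baseline to about 50% by the end of inpatient treatment, and section 2.2 gives controls insomnia education. Some of that pilot fall may precede this trial's baseline, which is taken from day 14 onward. Even so, a within-arm drop on SHUTi cannot simply be taken as the between-arm difference.
- **Sleep symptoms are a legitimate part of depressive severity.** The full total is the scale as described, with a cited internal consistency of 0.90. The documents give no such support for a shortened score, so replacing the total would go too far.
- **Readers will have the ISI and the Pittsburgh Sleep Quality Index beside the IDS.** These show whether sleep changed, but not how much of an IDS difference came from sleep items.

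The objections remove any claim of a known or large effect and any case for discarding the total. The inability to attribute an IDS difference to mood remains.

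**Conclusion.** The point holds as a limit on interpretation. The between-arm comparison of the IDS total is a valid randomised comparison. Without a score that leaves out the sleep items, a difference on it does not show a mood benefit separate from the insomnia effect.

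The size cannot be derived from the documents. The range of 0.17 to 0.80 SD, with an 8% to 77% chance of p<0.05, rests on the assumed item count, a between-arm sleep-item difference of 2 to 4 points, an assumed SD of 5 to 12, and the plan's ISI correlation and attrition carried over to the IDS. A difference below 2 points gives less. The documents do not support the stronger inference that the trial would report an antidepressant effect from sleep items alone; they show only that it could not rule this out.

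This is a minor matter. One secondary outcome is affected, and the primary outcomes and sample size are not.

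**What to change.** Keep the IDS total as the scored secondary outcome. In section 2.4, name the sleep items on the IDS form in use and define a second score that omits them. In section 3, prespecify the same mixed model for that score and state that both results will be reported side by side. Add one sentence on interpretation: an IDS effect will be described as an effect on mood independent of sleep only if the score without sleep items supports it. This should be fixed before any comparison by arm is seen, because a reduced score added afterwards would look selective.

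The cost is one scoring line and one extra model. Summing 28 responses already requires the item data, so nothing new is collected. The drawback is that the documents give no severity bands or reliability for the reduced score. The full total therefore remains the score for describing the sample and for comparison with other studies.

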Insomnia Severity Index (ISI). The ISI is a seven-item global index of self-reported insomnia symptom severity. It is valid, reliable, sensitive to changes in insomnia treatment (Bastien, Vallieres, & Morin, 2001; Morin, Belleville, Belanger, & Ivers, 2011) and validated for online use (Thorndike et al., 2011). Seyffert and colleagues (2016) categorized insomnia severity by scores as follows: 0-7 = no clinically significant insomnia, 8-14 = subthreshold insomnia, 15-21 = moderate insomnia, and 22-28 = severe insomnia. Changes in the ISI over time will be a primary outcome measure. The ISI is collected within the SHUTi intervention program at the beginning of each core, but participants in both Phase I and Phase II will also complete a paper version of the ISI during the pre-, mid-point, and post-test assessments.

Daily sleep and symptom diaries. Prospectively collected sleep diaries are a proven method for assessing insomnia and track treatment effects (Carney, et al., 2012; Buysse, Ancoli-Israel, Edinger, Lichstein, & Morin, 2006) and have been used for other sleep studies among patients on 1SE (inpatient and outpatient). Participants will be asked to complete at least five out of every seven days of daily sleep and symptom diaries. These diaries will include sleep/wake times, time in bed, sleep onset latency, number and duration of awakenings, sleep quality, naps, alcohol consumption, any over-the-counter or prescription medications used to help with sleep (participants will be instructed to include any marijuana use in this section), and open-ended comments. For the experimental group, diaries will be used to assess adherence to their “sleep window,” based on actual time in bed as a proportion of prescribed time in bed. We will cross-validate diary-reported sleep duration with actigraphy data when possible. Secondary outcome measures captured in the diaries will include a categorical measure of relapse (i.e. whether the participant reports any drinking post-discharge) as well as quantity and frequency of drinking, which will be calculated in the case of relapse, as well as all other diary variables.

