Composite Scale of Morningness (CSM). The Composite Scale of Morningness is a 13-item scale (Smith, Reilly, & Midkiff 1989). Questions address topics like morning affect, preferred sleep/wake times, and peak cognitive performance, with scores ranging from 13 (reflecting "eveningness") to 55 (reflecting "morningness"). The CSM typically shows relatively high internal consistency (Cronbach's alpha > 0.8) (Di Milia, Adan, Natale, & Randler 2013).

We will pull additional data from the screening/treatment protocol to characterize our sample and conduct exploratory analysis based on the aforementioned aims, including but not limited to:

- Childhood Trauma Questionnaire (CTQ)
- Structured Clinical Interview for Diagnostic and Statistical Manual of Mental Disorders (DSM-IV or DSM-5) (SCID)
- Clinical Institute Withdrawal Assessment – Alcohol revised (CIWA-Ar)
- Comprehensive Psychopathological Rating Scale (CPRS)

[figure not shown]

Figure 1: Study flow chart

Participants will be screened for eligibility on or after day 14 of inpatient treatment. Days 14-21 will be when the participant is consented, screened for OSA (after consent), randomized (if they meet inclusion requirements), and begin daily diary assessments as a baseline measure. If they are discharged before they are deemed eligible for continue study participation and randomized to a group, they will be removed from the study.

Table of Measures						
	Inpatient			Outpatient		
	Pre-Test (Before SHUT-i® Intervention or Education only program initiation)	Start SHUT-i® Intervention or Education only program	Prior to or within 2 weeks of Discharge	3-4 weeks after SHUT-i® Intervention or Education only program initiation	Post-Test (After SHUT-i® Intervention or Education only program completion)	6-7 months post-discharge (clinic visit or by phone)
ISI				X		X
PACS					X	X
PSQI	X			X	X	
DBAS-16	X				X	
FOSQ-10	X				X	
SE-S	X				X	
IDS	X				X	
ESS	X				X	
Trait Anxiety Inventory	X				X	
CSM	X					
MFSI-SF	X				X	
At least 4 days, 3 nights (Phase I)/1 week (Phase II) of actigraphy assessment	X			X	X	
Sleep Diaries	X			X	X	
Start SHUTi (Phase I and II) or education only (Phase II only) program		X				
Abbreviated Internet Evaluation and Utility Questionnaire (Phase I only)			X			

Protocol Number: 18-CC-0079

Internet Impact and Effectiveness Questionnaire, Internet Evaluation and Utility Questionnaire, and the Internet Intervention Adherence Questionnaire (Phase I and II)					X	

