Exit interview regarding experience with SHUTi program (Phase I only)					X	
Dichotomous Yes/No Relapse Assessment						X (If YES, TLFB will be administered)
TLFB						X

Protocol Number: 18-CC-0079

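### The 6-7 month TLFB depends on one Yes/No relapse answer, so drinking outside the diaries can be missed and a diary-positive participant can be classified two ways

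*Combined protocol and SAP*

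**What the plan says.** Section 1.2 (objective 2b) lists "alcohol consumed (post-discharge), alcohol craving (post-discharge" among the secondary outcomes and names no instrument for either.

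The diary paragraph of section 2.4 makes the diaries one source: "Secondary outcome measures captured in the diaries will include a categorical measure of relapse (i.e. whether the participant reports any drinking post-discharge", followed by "as well as quantity and frequency of drinking, which will be calculated in the case of relapse, as well as all other diary variables". On completeness it says: "Participants will be asked to complete at least five out of every seven days of daily sleep and symptom diaries".

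The Table of Measures in section 2.4 supplies a second source. Its last column, headed "6-7 months post-discharge (clinic visit or by phone", contains the row "Dichotomous Yes/No Relapse Assessment", and the cell reads "X (If YES, TLFB will be administered". The next row, TLFB, has an unconditional X in the same column. The diary row is marked at pre-test, at 3-4 weeks after program start and at post-test, with nothing at 6-7 months.

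The text of section 2.4 does not describe the TLFB or expand the abbreviation. It is taken here to be the Timeline Followback drinking interview. Neither section 2.4 nor section 3 says how the two sources are combined.

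**The concern.** Read with its note, the relapse row lets a No end the collection of drinking data at the last visit. The only other alcohol-related measure in that column is the PACS, which section 2.4 describes as a craving scale. It cannot reveal a drinking episode that the Yes/No answer missed.

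Two problems follow. First, a lapse after the diaries stop, or on a day with no entry, reaches the data only through that one answer. If it is forgotten or denied, relapse and quantity are both under-recorded for that person, and the two errors point the same way. Second, a participant with drinking in a post-discharge diary who answers No at 6-7 months has two contradictory relapse statuses and no TLFB to settle them or to cover the later months.

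Equal under-reporting in both arms would shrink a true difference. Unequal under-reporting could create one. The plan describes no blinding of participants to their program, so unequal reporting is possible, though nothing in the documents shows it.

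**Working it through.** **No figure to reproduce.** The documents give no relapse rate, error rate or power for drinking outcomes. The only power figure concerns the ISI. With 60 × (1 − 0.40) / 2 = 18 per arm and correlation 0.6, the detectable effect is (1.960 + 0.842) × √(2 × 2 × 0.4 / 18) = 0.835, which matches the stated 0.84. It has no bearing on relapse, apart from supplying 18 per arm as a working number below.

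**Coverage, from the sections side by side.**
- *A drinking day with a diary entry:* kept for relapse, quantity and frequency by the diary paragraph, whatever is answered at 6-7 months.
- *A day in the diary period without an entry:* the minimum of five days in seven permits 2/7 = 29% of days to be blank. These days depend on the Yes/No answer.
- *A day after post-test:* section 1 says a new SHUTi core opens seven days after the previous one is completed. Someone who keeps pace therefore finishes six cores in about 6 × 7 = 42 days, or six weeks. Section 2.2 has at least one core done as an inpatient, so the start precedes discharge. Taking six months as 26 weeks, at least 26 − 6 = 20 weeks before the visit have no scheduled drinking record other than the Yes/No answer and what follows from it. Slower users leave a shorter gap, since section 2.2 allows access for up to six months.
- *Diary shows drinking, answer is No:* relapsed by one source, abstinent by the other, no TLFB under the note, and no rule to decide.

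**Illustration of size.** All rates here are assumptions. Let *s* be the share of relapsers who answer Yes, with no false Yes answers. Observed relapse = true relapse × *s*.
- True relapse 60% vs 40%: at *s* = 0.95, 0.57 − 0.38 = 0.19; at *s* = 0.80, 0.48 − 0.32 = 0.16. A 20-point difference appears as 16-19 points.
- Relapsers answering No, 18 reached per arm: 18 × (0.60 + 0.40) × (1 − *s*) = 0.9 at *s* = 0.95 and 3.6 at *s* = 0.80. If all 60 were reached (30 per arm), 1.5 to 6.0.
- Equal true relapse of 60%, *s* = 0.80 in one arm and 0.90 in the other: 0.48 vs 0.54, a spurious 6 points. Equal true relapse of 50%, *s* = 0.70 vs 0.90: 0.35 vs 0.45, a spurious 10 points.

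These figures assume that the diaries caught none of the missed lapses, so they apply only to drinking outside the diary record. The 18 per arm borrows the attrition assumed for the ISI calculation, which is not a stated follow-up rate for the 6-7 month visit.

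**Scale against sampling error.** With 18 per arm at 60% vs 40%, the standard error of the difference is √(0.24/18 + 0.24/18) = 0.163, so the 95% half-width is 1.96 × 0.163 = 32 points. Power for a two-sided 5% test with pooled null variance is about 22% at *s* = 1 and 16% at *s* = 0.80.

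**The case against.** A reader might infer that a lapse already written in a diary is lost from both relapse and alcohol consumed once the participant answers No. The documents do not support that. The diary paragraph takes relapse, quantity and frequency from the diaries, so such a lapse remains outcome data. What is missing is the TLFB for that person and a rule for the conflict.

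Other counterarguments carry weight:
- The TLFB row has an X with no condition, so giving it only after a Yes is not beyond doubt. The note is nevertheless the only stated rule. If the TLFB was meant for everyone, the note is what needs correcting.
- The wording, prompts and recall window of the relapse assessment are not given. Section 10 has follow-up assessments administered by research staff, so probing is possible. It is one dichotomous assessment, but its sensitivity is unknown.
- Skipping a detailed interview after a No is an ordinary way to save burden, and the TLFB is itself self-report at the same visit. Someone who conceals drinking on the first question can conceal it on the second. This limits the benefit largely to forgotten lapses.
- The illustrated distortions are small beside a half-width of about 32 points, and no reason is given why these two programs would change denial of drinking.

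None of this supplies a rule for combining the sources, or a second measure of drinking for the months after the diaries stop.

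**Conclusion.** The point stands as a gap in the capture and definition of secondary outcomes. If the note in the relapse row governs, drinking after post-test or on days without a diary entry rests on one Yes/No assessment, and a diary-positive participant who answers No has an undefined relapse status. The two table rows also disagree on their face.

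The size of the under-count cannot be derived from the documents. The 16-19 point and 6-10 point figures rest wholly on assumed relapse rates and sensitivities, and concern only drinking the diaries did not catch. They show direction and rough scale; they are not an estimate of bias in this trial. Differential misreporting between arms is a possibility, not a finding. The primary outcomes are unaffected. The change is still worth making because it is cheap and because analysis cannot recover drinking that was never recorded.

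**What to change.** 1. Reconcile the two rows of the Table of Measures: give the TLFB, covering discharge to the visit, to every participant reached at 6-7 months, whatever the Yes/No answer. At minimum, also give it to anyone whose post-discharge diary shows drinking.
2. Define relapse in section 2.4 or section 3 as yes if the Yes/No assessment, the TLFB or a post-discharge diary shows drinking. This settles the participant whose diary is positive and whose answer is No.
3. State which source defines alcohol consumed where diary and TLFB periods overlap, and how the amount is recorded when no TLFB is given.

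The cost is a wording change to the table and text, plus a few interview minutes for participants who answer No. No new instrument or visit is needed. The change mainly recovers forgotten lapses and does not remove deliberate denial. It should be made before further 6-7 month visits take place.
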